#### 6.1.2 The Study Eye (SE)

The Study Eye (SE) will be determined by the Investigator prior to the clinical trial as eligibility for the study required a planned DWEK/DSO procedure planned for the medical management of the patient. The SE is defined as the eye that was selected by the treating physician for surgical intervention of DWEK/DSO and the eye to which TTHX1114 is administered (if applicable).

If a study subject wishes to undergo DWEK/DSO in the Fellow Eye after the SE has recovered, the subject may be re-enrolled in Group 3 or Group 4 and the contralateral eye may be treated. "Recovery" is based on the Investigator discretion following the primary efficacy endpoint evaluation on Day 28 (e.g., BCVA of at least 20/40 or have a measured CCT of less than a 10% increase from baseline). Planned treatment of all contralateral eyes must be discussed with and approved by the Sponsor (or designee) prior to treatment.

[figure not shown]
### 6.1.3 Subject Registration

Prior to enrollment, study subjects in all treatment groups must be registered and approved for enrollment. At a minimum, the investigational site will complete the Subject Registration Form (Subject ID number, planned date of DWEK/DSO, etc.) and an eligibility checklist (including prior participation in Study TTHX-001 or Study TTHX-002, if applicable). Following registration, approval of enrollment, and treatment group assignment, investigational product will be requested and shipped to the investigational site.

# 6.2 Study Treatment Administration/Intracameral Injection

[figure not shown]
This procedure can be performed by a qualified and trained ophthalmologist who is familiar with DWEK/DSO and who has been trained on TTHX1114 administration.

### Materials:

Confidential and Proprietary

Amendment 7.0: September 22, 2022

[figure not shown]

[figure not shown]
# Procedure Study Day 0:

Amendment 7.0: September 22, 2022

[figure not shown]
Figure 4: Intracameral Injection Entry Point

# 6.2.2 Subsequent TTHX1114 Administrations

Following the Day 0 TTHX1114 administration, subsequent weekly administrations will occur approximately every 7 days  $\pm 1$  day. If a study treatment administration cannot be administered within the 6 to 8 days following the prior administration, the study treatment may be delayed, and the scheduling of all remaining administrations adjusted to ensure that TTHX1114 is not administered fewer than 5 days after the prior administration.

Confidential and Proprietary

Amendment 7.0: September 22, 2022

#### 6.3 Concomitant Medications and Treatments

#### 6.3.1 Concomitant Medications

Subjects are expected to receive concomitant medications for the management of concurrent medical conditions. Medications taken during the 28 days prior until 28 days following the last study treatment administration will be recorded. Artificial tears are allowed during the study, but other ocular medications must be discussed with the masked Medical Monitor.

#### 6.3.2 Prohibited Medications

The following medications are prohibited unless approved by the Medical Monitor:

Subjects requiring the use of prohibited medications must be discussed with the Medical Monitor.

### 6.3.3 Pregnancy Testing and Contraception

Women of child-bearing potential (WOCBP) are defined as a premenopausal female capable of becoming pregnant. Women who are not WOCBP are those who have not had a menstrual cycle for at least 2 years or who have had hysterectomy, bilateral tubal ligation, or bilateral oophorectomy. Sexually active female subjects who are WOCBP must use at least 1 highly-effective method of contraception or at least 2 less effective methods of contraception (including 1 barrier method), starting at least 1 month prior to Day 0, and male subjects who are sexually active with women of childbearing potential must agree to use a double-barrier method of contraception. Per *ICH M3(R2) Non-Clinical Safety Studies for the Conduct of Human Clinical Trials and Marketing Authorization for Pharmaceuticals*, highly-effective methods are defined as "those, alone or in combination, that result in a low failure rate (i.e., less than 1% per year) when used consistently and correctly." FDA-approved contraceptive methods and estimated failure rates are summarized in Table 8.

Amendment 7.0: September 22, 2022

Table 8: FDA-Approved Methods of Contraception and Estimated Failure Rates

Method	Failure Rate
Highly-Effective*	
Sterilization surgery for women	Less than 1%
Sterilization implant for women	Less than 1%
Sterilization surgery for men	Less than 1%
IUD Copper	Less than 1%
IUD with Progestin	Less than 1%
Implantable Rod	Less than 1%
Less-Effective	
Shot/ Injection	6%

 
Oral Contraceptives "The Pill" *
 
	9%
• Patch	9%

 
Vaginal Contraceptive Ring
 
	12%
Diaphragm with Spermicide	12-24%
Cervical Cap with Spermicide	17-23%
Male Condom	18%
Female Condom	21%
Spermicide Alone	28%

\*(including Combined, Extended/ Continuous Use Combined Pill, and the "Mini Pill", Progestin only)
Adapted from FDA Birth Control Guide www.FDA.gov/birthcontrol

The contraceptive plan for each subject should be discussed with the Investigator and will be determined at the Investigator's discretion including the use of a double barrier (e.g., male condom, female diaphragm with spermicide) in male subjects.

### **6.4 Study Procedures**

All study procedures/ visits should be performed at the designated timepoint (within the protocol-specified window, if applicable). If an assessment/ visit cannot be collected/ performed within the protocol-specified parameters, it should be collected as soon as practicable, and the actual date/ time/ reason recorded.

#### 6.4.1 Informed Consent

A sample Informed Consent Form (ICF) will be provided by Trefoil and will be in accordance with 21 CFR 312 Part 50 Subpart B Section 50.25. The sample ICF will be revised by the investigational site to include site-specific information and required language, as needed. The Investigator ensure IRB/IEC review and approval of ICF. Written informed consent will be obtained from all potential subjects prior to any study-specific assessments are conducted. Informed consent will be obtained in accordance with 21 CFR Part 50 Protection of Human Subjects and may be obtained any time prior to the start of study-specific assessments.

Alternative therapies will be discussed with each potential participant including other pharmacologic therapies, investigational treatments (if available), or watchful waiting. Informed consent will include a HIPAA release/ waiver.

### 6.4.2 Demographics

Demographic information will be recorded, including:

Confidential and Proprietary

Amendment 7.0: September 22, 2022

[figure not shown]
- Age
- Sex
- Race
- Ethnicity

The subject's height and weight will be measured and recorded. Height should be measured without shoes and weight should be measured with minimal street clothing. If the Investigator feels that the subject is a reliable source, self-reported height and weight may be recorded.

### 6.4.3 Medical History and Ocular History

During the Screening/ Pretreatment Period, the Investigator (or designee) will review the medical history of all potential subjects to document all relevant clinically significant baseline medical conditions, concomitant medication use, and to determine study eligibility. Medical History Assessment will include review of all available medical records and patient interview. Assessment of all eligibility criteria should be evidenced in the study records. Medical history will include a detailed disease history regarding onset, severity, and history of prior therapy.

In addition to the data collected in demographics and medical history, specific information will be collected regarding each subject's ocular history, including:

### 6.4.4 Comprehensive Ocular Examination

A comprehensive ocular examination will include slit-lamp biomicroscopy and a dilated examination of the lens, fundus (retina, optic disc, macula, fovea, and posterior pole), and vitreous.

[figure not shown]
The comprehensive ocular examination should also include baseline macular optical coherence tomography (Mac-OCT). As BCVA is the primary efficacy measurement in the study, it is important to identify any macular pathology or other confounding co-morbidities.

Confidential and Proprietary

Amendment 7.0: September 22, 2022

[figure not shown]

### 6.4.6 Specular Microscopy

Specular microscopy images will be obtained of the periphery and center of the cornea. The center of the cornea is defined as the region of the cornea above the pupil. If a subject is to be dilated at a visit, specular microscopy should be performed prior to dilation. To address differences in location of the image within a given area of the cornea, five acceptable images should be taken at each required timepoint. Peripheral images will be collected at the screening visit; central images will be collected at prior to treatment and whenever possible following treatment. Due to the nature of corneal edema following DSO, specular microscopy images may not be able to be obtained at all post-operative timepoint prior the deturgescence of the cornea. Attempts should be made to collect images at all timepoints; if images are unable to be obtained, the reason for not being able to collect images will be recorded. If specular microscopy images are obtainable, it is expected that images will remain obtainable at all subsequent timepoints. Prior to the end of each specular microscopy session, the technician should review the images to ensure that the captured images are of the highest quality obtainable. Subjects with inadequate images may be required to return to the investigational site for repeat imaging as an unscheduled visit.

Endothelial cell density, percent hexagonality and the coefficient of variation will be assessed from specular microscope images.

Cornea Image Analysis Reading Center (CIARC) at University Hospitals Cleveland Medical Center will function as the centralized reading center and will be responsible for the certification of equipment and training of technicians as well as reading images and conducting image analysis. If more than one specular microscope is installed at a site, the same specular microscope will be used for all visits for a given patient.

Clinical Study Protocol TTHX-002

[figure not shown]
Trefoil Therapeutics, Inc.

Confidential and Proprietary

[figure not shown]
Amendment 7.0: September 22, 2022

Baseline images and on-study central images will be sent to CIARC; baseline images will be archived, and on-study images will be assessed for efficacy.

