#### 3. TRIAL OBJECTIVES AND PURPOSE

The primary objective of this clinical trial is to evaluate the safety and efficacy of TTHX1114 in the setting of DWEK/DSO. The primary efficacy endpoint will include CEC counts/ characteristics and BCVA following the surgical procedure.

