#### 7. ASSESSMENT OF EFFICACY

As described above, the efficacy endpoints will be visual acuity and endothelial cell count/density as measures by specular microscopy. Other efficacy assessments include:

- Slit lamp biomicroscopy assessments
- Central corneal thickness
- IOP

The primary efficacy timepoint is Day 28.

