**Table 12: Analysis Sets** 

Analysis Set	Description of Population	Reference
Full Analysis Set*	
 
Received any study treatment (at least 1 complete or partial dose)
 
	ICH E9 (5.2.1)
Per Protocol Set	Met all eligibility criteria	ICH E9 (5.2.2)
	Have received all study treatments per protocol	
	
 
Underwent DWEK/DSO of 4 to 5mm
 
	
	
 
Have sufficient data collected for the accurate assessment of study endpoints
 
	

\*The Full Analysis Set will be used for the Safety Population

The Per Protocol Population will be used to assess the primary and secondary efficacy endpoints compared to the control group.

The Safety Population set includes all participants in participants who received any TTHX1114 and will be the population for safety outcomes; this population will be compared with the control group. Ocular AEs involving the study eye will be tabulated. Ocular AEs for the fellow eye and non-ocular AEs will be provided as a listing.

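### Day 28 endothelial cell density may be missing because the eye has not recovered, and the open-ended data condition of the Per Protocol Set permits dropping such eyes from visual acuity and corneal thickness too

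*Combined protocol and SAP*

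**What the plan says.** **Where density comes from.** Section 6.4.6: "Endothelial cell density, percent hexagonality and the coefficient of variation will be assessed from specular microscope images". The same section says that, because of edema after the procedure, "specular microscopy images may not be able to be obtained at all post-operative timepoint prior the deturgescence of the cornea". It asks for attempts at every timepoint, has the reason for a missing image recorded, expects images to stay obtainable once they have become so, and allows repeat imaging at an unscheduled visit.

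**Status of density.** Section 3: "The primary efficacy endpoint will include CEC counts/ characteristics and BCVA following the surgical procedure". Section 7: "the efficacy endpoints will be visual acuity and endothelial cell count/density as measures by specular microscopy", and "The primary efficacy timepoint is Day 28". Section 4.1, however, visibly lists only BCVA of 20/40 or better and central corneal thickness (CCT) at Day 28, and Section 6.4.4 treats BCVA as the primary measure.

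**Who is analysed.** Section 9.3.1: "The Per Protocol Population will be used to assess the primary and secondary efficacy endpoints compared to the control group". One condition for that set in Table 12 is "Have sufficient data collected for the accurate assessment of study endpoints". Nothing says which endpoint or visit it refers to. The Full Analysis Set contains dosed subjects only, so an undosed Group 1 control is outside it.

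**How it is summarised.** Section 9.2 gives continuous variables as sample size, mean and SD, median, minimum and maximum. No missing-data rule is stated; LOCF and MMRM appear only in the abbreviation list. Section 9.3 defers detail to an SAP, and no SAP text is in the material available.

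**The concern.** Under Section 6.4.6, whether an eye has a Day 28 density depends partly on whether its cornea has cleared, and clearing is part of what the treatment is meant to achieve. The protocol expects some eyes to be unrecovered by then: Group 4 has a provision for subjects not sufficiently recovered at Day 28, and Section 6.4.11 covers delayed recovery at Days 28 and 56. Two consequences follow.

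- **Density.** A mean over gradeable eyes describes the eyes that did better. It overstates each group's density. If one regimen clears more marginal corneas than another, those eyes enter its own average and pull it down, so the difference between regimens shrinks.
- **BCVA and CCT.** The Table 12 condition speaks of endpoints in general. On one permitted reading, an eye without a gradeable image lacks data for one study endpoint and leaves the set, taking its BCVA failure and thick cornea with it. Per-group 20/40 rates would then be inflated. In an open-label study with an undefined condition, that choice could be made after outcomes are known.

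**Working it through.** The plan has no figure of its own to reproduce here. The documents give no gradeable proportion, density mean or SD, or success rate, and Section 9.1 says the sample size was not statistically derived. **Every input below except the planned group size of 20 is an assumption**, chosen to show mechanism and range.

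**1. Density, single example.** Assume true Day 28 central density with means 700 and 850 cells/mm² in two groups, SD 300, and an image gradeable when density plus independent noise (SD 150) exceeds 500.

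- SD of density plus noise: √(300² + 150²) = 335.4.
- Proportion gradeable = Φ((mean − 500)/335.4): Φ(0.596) = 72.5% and Φ(1.043) = 85.2%.
- Mean in gradeable eyes = mean + (300²/335.4) × φ(z)/Φ(z), with z = (mean − 500)/335.4 and 300²/335.4 = 268.3.
  - Weaker group: 700 + 268.3 × 0.334/0.725 ≈ 824.
  - Stronger group: 850 + 268.3 × 0.231/0.852 ≈ 923.
- Observed difference: 923 − 824 = 99, against a true 150. About one third is lost, and the means are overstated by 124 and 73.

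**2. Density, range.** A second model works in SD units. Density is seen only if a clearing variable, correlated ρ with it, passes a threshold; the treatment shifts both by d. With d = 0.5 to 1.0, lower-arm clearing 30% to 70% and ρ = 0.5 to 1.0, the difference in gradeable eyes is 31% (d = 0.5, clearing 30%, ρ = 1.0) to 82% (d = 1.0, clearing 70%, ρ = 0.5) of the true one.

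**3. 20/40 rate within a group, if ungradeable eyes are removed.** Let a share m of eyes be ungradeable, with success 75% in gradeable eyes and s = 15% to 30% in ungradeable ones. All-eye rate = (1 − m) × 0.75 + m × s. The gradeable-only report is always 75%.

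| m | all-eye rate, s = 15% | all-eye rate, s = 30% |
|---|---|---|
| 10% | 69% | 70.5% |
| 20% | 63% | 66% |
| 30% | 57% | 61.5% |

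In a group of 20, the size planned for Groups 3 and 4, m = 20% means 16 gradeable eyes with 12 expected successes, and 4 removed eyes with 0.6 to 1.2. The full result is 12.6 to 13.2 of 20, or 63% to 66%.

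**4. 20/40 difference between two groups, same exclusion.** Assume 50% and 80% of eyes clear, with success 80% if cleared and 10% if not, the same in both groups.

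- All eyes: 0.5 × 0.8 + 0.5 × 0.1 = 45%; 0.8 × 0.8 + 0.2 × 0.1 = 66%. Difference 21 points.
- Half the uncleared eyes removed: 0.425/0.75 = 56.7%; 0.65/0.90 = 72.2%. Difference 15.6 points.
- All uncleared eyes removed: 80% and 80%. Difference 0.

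The exact zero follows from assuming equal success once cleared. The direction is the point: within-group rates rise while the difference falls.

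**5. Existing safeguards.** A recorded reason has no analysis rule attached. Repeat imaging need not yield a Day 28 value in an eye that is still edematous. The demand for gradeable images in the End of Study section concerns the last visit. None of these supplies the missing Day 28 density.

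**The case against.** **A stronger reading is tempting.** A reader might infer that density can be read only after edema clears, so that unhealed eyes necessarily drop out of the whole Day 28 efficacy result. The documents do not support that.

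- Section 6.4.6 says images may be unobtainable, not that they always are. An image can also be missing or inadequate for other reasons.
- Reading the sufficiency condition endpoint by endpoint is at least as natural. BCVA and CCT need no specular image, and Sections 6.1.1 and 6.4.11 keep working up eyes with delayed recovery. The calculations for 20/40 rates depend wholly on the other reading.
- Density's rank is unsettled: Sections 3 and 7 include it, while Sections 4.1 and 6.4.4 put BCVA and CCT forward. The additional-endpoint list in Section 4.1 is blank in the text supplied, so nothing can be inferred from its absence.
- Section 9.2 already plans the sample size and median, so the number of contributing eyes would be visible.
- An SAP may contain the missing rules.
- Group 1 closed after one subject (Table 7), so comparison with control is barely estimable under any rule. Where the bias does affect a density comparison, under these assumptions it runs toward no difference.

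**What stands of this.** These points limit scope and severity. They do not remove the problem. A median over gradeable eyes is still a median of recovered eyes, and a sample size reveals missing images without separating edema from other causes. Table 12 leaves the harmful reading open. The Full Analysis Set is not the assigned efficacy population and excludes undosed controls.

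**Conclusion.** The point holds in a limited form and should be fixed; it is not a fatal flaw. For density, missingness at Day 28 can depend on recovery, and the visible plan summarises whatever is gradeable. Under the assumptions shown, within-group means are overstated by about 70 to 125 cells/mm², and only 31% to 82% of a true difference remains across the range examined (about two thirds in the single example).

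For BCVA and CCT, the loss of unrecovered eyes is permitted by Table 12 but not required. If it happened, a reported 75% success rate could stand for an all-eye rate of 57% to 71% when 10% to 30% of eyes are removed. These figures show direction and possible size; the documents give nothing from which to estimate the actual share of ungradeable eyes.

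With a single control enrolled, the practical exposure is to within-group rates, above all in Groups 3 and 4, and to comparisons among the active groups. A claim that the treatment effect against control is distorted by a known amount would go beyond the documents.

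**What to change.** Amend Table 12 and Section 9.3, and carry the same text into the SAP, before database lock:

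1. Apply the sufficiency condition separately to each endpoint. State that an image unobtainable because of corneal edema is not a reason to leave the Per Protocol Set, so the eye stays in the BCVA and CCT analyses.
2. For each group, report the number and proportion of all Per Protocol eyes with a gradeable central image at Day 28, split by the reason for a missing image already recorded under Section 6.4.6.
3. Pre-specify a Day 28 density analysis that ranks edema-ungradeable eyes worst, reported as a median with a rank-based comparison. If half or more of a group is ungradeable, report the median as not measurable; the ranks can still be compared. Treat images missing for other reasons as ordinary missing data. Keep the gradeable-eye mean as descriptive.

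The cost is wording and programming; no new data are needed. The downside is small: per-group figures may look less favourable, and the density result becomes rank-based, which is harder to express in cells/mm².

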Amendment 6.0	
 
To add an Optional Extended Dosing Period OEDP for subjects who have received fewer than 5 TTHX1114 administrations
 
To add 2 additional dose levels to be explored in dose-escalation
 
To add additional detail around dose-escalation rules
 
To add clarification regarding nomenclature related to Study Eye and Fellow Eye
 
To change the distribution of subjects in each group and decrease the overall number of subjects in the trial
 
To update the definition of efficacy endpoints to align with the Statistical Analysis Plan
 
Provide additional guidance related to eligibility regarding allergy history
 
Clarify that peripheral specular images will be collected at baseline and sent to CIARC for archiving
 
Clarify that the average IOP measurement will be recorded at each required timepoint
 
Add definitions for Adverse Events of Special Interest
 
Update Per Protocol Population definition
 
The protocol was revised for the following reasons:
 
To modify the exclusion of prior refractive surgery in the study eye unless approved by the Sponsor
 
To remove reference to 75ng dose and dose escalation during the OEDP
 
To clarify that the planned and actual area of descemetorhexis area is 4 to 5mm and to specify that subject with a descemetorhexis area of > 5mm will be excluded from efficacy analyses
 
To require the reporting of the reasons for changes in study procedures
 
To add the provision of AS-OCT imaging at least once post-operatively to confirm the size of descemetorhexis area
 
To clarify that specular microscopy images will be collected at designated timepoint, when possible
 
To allow alternate methods of measuring CCT within a subject
 
To provide additional guidance regarding ocular assessments for subjects with delayed recovery
 
Update Per Protocol Population definition

Amendment 7.0	The protocol was revised to:
Amendment 7.0	
 
Remove reference to the Optional Extended Dosing Period (OEDP) that was not implemented
 
Include an End of Study (EOS) Visit for all subjects that includes Assessments scheduled for Day 336 and a plasma sample for ADA
 
Correct the typo in Section 8.3 clarifying that all deaths occurring with 1 year of study treatment (not 28 days) are to be reported as AEs of Special Interest (AESI)
 

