#### 6.1 Subject Screening and Enrollment

Potential study participants will be asked to sign an Informed Consent Form (ICF) prior to any study assessments. Screening should be completed within approximately 28 days of Study Day 0 (unless approved by the Medical Monitor); non-qualifying screening assessments (e.g., specular microscopy) and screening assessments outside this window may be repeated. Screening assessments will include:

Assessment of study eligibility

Confidential and Proprietary

Amendment 7.0: September 22, 2022

- Medical and ocular history
- BCVA assessment
- Comprehensive ocular examination (including slit lamp biomicroscopy and dilated examination of lens, fundus, and vitreous)
- Specular microscopy (including images of the central and peripheral cornea)

All potential study subjects will be provided with a unique Subject ID Number (Subject ID) at the time of providing written informed consent. The Subject ID will consist of a unique 6-digit number (3-digit site number and a 3-digit subject number, separated by a hyphen [-]).

Figure 3: Subject ID Numbering

Subject ID Number						
Site Number			=	Subject Number		
9	9	9	-	2	0	1

For example, Subject ID 101-201 = The first participant consented at Site 101; 103-203 = The third participant consented at Site 103

Once a Subject ID number has been issued, it cannot be reused. Potential subjects may have repeat eligibility assessments (if appropriate) or be rescreened, following discussion with the Medical Monitor (or designee).

Subjects who had participate in Study TTHX-001 will receive a new Subject ID number for identification in Study TTHX-002. Subjects who "roll-over" to Group 1a or Group 3a will retain the same Subject ID number.

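### Baseline specular images are archived rather than graded, so no reading-center baseline endothelial density is specified for a named efficacy endpoint in a non-randomised study

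*Combined protocol and SAP*

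**What the plan says.** Section 6.4.6 of the protocol sets the imaging plan: "Peripheral images will be collected at the screening visit; central images will be collected at prior to treatment and whenever possible following treatment". On destination and use it says "Baseline images and on-study central images will be sent to CIARC", and then "baseline images will be archived, and on-study images will be assessed for efficacy". The same section says, without naming a visit, that "Endothelial cell density, percent hexagonality and the coefficient of variation will be assessed from specular microscope images".

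Section 7 says that "the efficacy endpoints will be visual acuity and endothelial cell count/density as measures by specular microscopy", with Day 28 as the primary efficacy timepoint. Section 3 also puts cell counts and characteristics in the primary efficacy endpoint. Neither section defines the cell endpoint as a change from baseline.

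Section 9.3.1 states that the study is open label and not randomised. Section 4 assigns subjects to whichever group is open when the eye is treated. Section 9.3 defers the analysis to a SAP to be written before database lock, and no text of that SAP is in the public document.

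**The concern.** Section 6.4.6 gives each class of image its own use: storage for baseline, efficacy assessment for on-study. Peripheral images are planned only at screening. If they are not graded, the reading center will hold no peripheral density for any eye at any visit.

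Nothing in the design balances endothelial reserve between groups:

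- Group 1 takes subjects who decline the drug or lack a qualifying fellow eye (Section 4).
- Groups 3 and 4 could open only after a preliminary look at Group 2 (Section 4).
- Subjects who received active drug in TTHX-001 may enter Group 3 but no other group (Section 5).
- The Document History records, as history only, that Amendment 2.1 dropped the minimum cell count in favour of investigator judgement and also added Group 3. Reserve may therefore differ between earlier and later enrollees.

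Without a graded baseline, a Day 28 density difference between groups could reflect reserve that the eyes brought with them, and the trial could neither check nor adjust for it.

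**Working it through.** **The plan's own figure.** The only sample size figure is 16 active against 8 control (Section 9.1), set on clinical and practical grounds. No alpha, power, SD or effect size is given, so there is nothing to reproduce. Everything below is illustrative, in SD units.

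**Reading the text.** Two readings of Section 6.4.6 are possible.

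- *Baseline images* means all of them: neither central nor peripheral baseline density is provided for.
- It means peripheral images only, as the Document History suggests ("Clarify that peripheral specular images will be collected at baseline and sent to CIARC for archiving"): central baseline density may be graded, but peripheral density is not.

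Peripheral reserve goes ungraded by the center on both readings. It is also the more useful covariate: Section 6.1.1 describes stripping a 4 to 5 mm area, so a pre-operative central count largely describes tissue that surgery removes.

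**Precision.** The active groups planned at equal size are Groups 3 and 4, with 20 each (Table 7).

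- Unadjusted 95% half-width: t(38) × sqrt(1/20 + 1/20) = 2.024 × 0.316 = 0.64 SD.
- With a baseline covariate of within-group correlation r, multiply by sqrt(1 − r²).

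| r (assumed) | sqrt(1 − r²) | Half-width | Shorter by |
|---|---|---|---|
| 0.3 | 0.954 | 0.61 SD | 5% |
| 0.5 | 0.866 | 0.55 SD | 13% |
| 0.7 | 0.714 | 0.46 SD | 29% |

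**Bias.** An unadjusted difference is biased by r × d, where d is the baseline imbalance in SD. With d = 0.5 (assumed), this is 0.15, 0.25 and 0.35 SD for r = 0.3, 0.5 and 0.7.

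**The two gains do not add in full.** If the 0.5 SD imbalance is present, the adjusted standard error grows by sqrt(1 + (0.25/38)/0.1) = sqrt(1.066) = 1.03. The half-widths become about 0.63, 0.57 and 0.47 SD. At r = 0.3 the gain is then only about 1.5% (0.954 × 1.032 = 0.985).

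**Control comparison.** Assume two-sided alpha 0.05 and 80% power, so the multiplier is 1.960 + 0.842 = 2.802.

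- Planned 16 against 8: 2.802 × sqrt(1/8 + 1/16) = 1.21 SD detectable.
- One control, as enrolled, against 20: 2.802 × sqrt(1 + 1/20) = 2.87 SD. Adjusted, this is 2.74 SD at r = 0.3 and 2.05 SD at r = 0.7.

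A comparison that can detect only effects above 2 SD is not rescued by adjustment.

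**Reading load.** Table 7 gives 1 + 9 + 20 + 20 = 50 subjects. The number of treated second eyes is not stated; allowing up to 15 (assumed) gives 50 to 65 image sets.

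**The case against.** The strongest case against is that the text does not say the baseline images go unread. The sentence on density, hexagonality and coefficient of variation is not limited to on-study visits, and Section 4.7 imports reading-center counts without naming visits. Central images are taken before treatment, and the Document History points to archiving of peripheral images only. Section 6.1 says "non-qualifying screening assessments (e.g., specular microscopy) and screening assessments outside this window may be repeated", so someone evaluates screening images for eligibility, and a site-read count may be recorded. The eligibility criteria, the additional endpoints in Section 4.1 and the SAP are not available to check. Section 4.1 lists BCVA and central corneal thickness at Day 28, and Section 6.4.4 calls BCVA the primary efficacy measurement, so cell density may carry less weight than Section 7 suggests. Finally, no document supports any particular r; it could be near zero.

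Much of this stands. A reader might infer that the cell endpoint has no baseline at all, or that its Day 28 results cannot be interpreted. The documents do not support that. Archived images remain gradeable, the endpoint is not defined as a change from baseline, and post-operative values can be compared between groups without one, though less securely.

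The objection does not supply a provision for a center-graded baseline density. The sentence that separates baseline from on-study images is the more specific one, and a site's eligibility review is not a reading-center value. A later SAP can use a center-read baseline only if the center grades the images. If r is near zero, neither the precision gain nor the bias arises, but a table of baseline density by group would still show whether the groups were comparable.

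**Conclusion.** The point holds as a low-cost improvement. The protocol specifies archiving, not efficacy grading, of baseline images and names no reading-center baseline density for an efficacy endpoint in a non-randomised study. On the narrowest reading, the gap is peripheral reserve.

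For 20 readable eyes per group and r = 0.3 to 0.7, the benefit is a half-width of 0.61 to 0.46 SD in place of 0.64 SD, and protection against a bias of 0.15 to 0.35 SD if reserve differs by 0.5 SD. The correlation, the imbalance and full readability are all assumptions. The figures are less favourable if r is lower or fewer eyes are readable, and Section 6.4.6 itself warns that edema may prevent post-operative imaging.

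The benefit applies to comparisons among the active groups, chiefly Groups 3 and 4, a contrast that the readable text does not itself specify. It does not extend to the single control subject, and the SD figures do not carry over to the binary BCVA endpoint.

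**What to change.** - Amend Section 6.4.6 so that the reading center grades the stored baseline images, peripheral first and central where gradeable, masked to treatment group. If central baseline images were always meant to be graded, say so and state which images are archived only.
- Report baseline density by group, with the number of ungradeable or missing images in each.
- In the SAP, specify baseline peripheral density as a covariate in the Day 28 cell-density comparison among the active groups. Groups 3 and 4 are the natural pair, because their schedules (Tables 3 and 4) list peripheral screening images. Include Group 2 where such images exist.
- Show the unadjusted comparison alongside, so that eyes without a gradeable baseline are not lost from view.
- Treat adjustment of central corneal thickness and BCVA for baseline density as sensitivity analyses only.

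The cost is reading time for about 50 to 65 stored image sets at the center that already receives them. No new reader, visit or procedure is needed. Some sets may prove ungradeable, and those eyes will have no covariate value.
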